3.3 Discussion of Study Design and Choice of Control Group(s)

3.3.1 Study Design

This open-label, prospective, non-controlled, international, multi-centre phase 3 study is designed to evaluate the efficacy of *wilate* in bleeding prophylaxis in paediatric patients below 6 years of age with severe VWD.

There is currently no data available on the tABR of patients <6 years of age with VWD undergoing regular prophylaxis. Description of the effect of prophylaxis on the tABR of patients with inherited coagulation disorders has been used as an efficacy endpoint to evaluate the clinical benefit of this intervention.

3.3.2 Control Group(s)

Not applicable.

3.3.3 Study Parameters

For the evaluation of efficacy endpoints, the following parameters will be documented:

1. *wilate* Consumption Data

- Dates and times of *wilate* injections
- Doses of *wilate* in IU and *wilate* batch numbers. IU/kg BW per injection, per month, and per year will be calculated.
- Purpose of *wilate* injection (PK/incremental in vivo recovery [IVR], prophylaxis, prophylaxis to avoid re-bleeding, treatment of BE, surgical prophylaxis)

2. *Assessment of Adherence with the Treatment Regimen*

Adherence with the treatment regimen will be assessed throughout the study. Any change of the prophylactic dose as determined by the responsible treating Investigator during the PK Visit will be documented in the patient records and electronic Case Report Form (eCRF), including start and end dates of each dose and the reason for dose change.

3. *Efficacy Assessment in Treatment of BEs*

Details of each (treated and not treated) BE will be recorded:

- BE type (spontaneous, traumatic, postoperative, other)
- BE location
- BE severity (minor or major) (Table 2)
- Date and time the BE first occurred or was first noticed
- Date and time the BE ended
- *wilate* administration data, if applicable
- Assessment of the efficacy of treatment at the end of the BE, if applicable

All parameters will be documented in a patient diary by the patient's parent(s)/legal guardian(s) (hereafter referred to as "parents"), or in the case of on-site treatments with the responsible treating Investigator, and in the case of use of a home-care service together with the nurse.

Table 2 Definition of the Severity of Bleeding

Bleeding severity	Description
Minor	Mild haemarthrosis (mild swelling, 'aura,' pain, warmth of the skin over the joint, change in range of motion, decrease in mobility and activity, slight difficulty in using the limb compared with baseline), superficial muscle bleed (pain and/or swelling and functional impairment compared with baseline), soft-tissue bleeding (scrapes, superficial cuts such as those cause by shaving razor, knife, or scissors, bleeding episodes that require frequent bandage changes, cutaneous bleeds with numerous bruises >1 cm), oral bleeding (superficial mouth bleeds, oozing or bleeding related to tooth eruption or extraction, spontaneous or after brushing/flossing, gum bleeding, bleeding after bites to lip or tongue), and most nose bleeds (i.e., those causing distress or interference with daily or social activities).

Bleeding severity	Description
Major	Generally requires hospitalisation; causes incapacity, significant pain, and substantial decrease in range of motion of affected joint (in case of joint bleeds); includes symptomatic bleeding in a critical area or organ (such as intracranial, intraspinal, intraocular, retroperitoneal, intraabdominal, intraarticular, or pericardial bleeds), intramuscular bleeds with compartment syndrome, bleeds of the pelvic muscles, periorbital bleeds, gastrointestinal bleeds, central nervous system bleeds, bleeding in the area of the neck or throat or pharynx, other major trauma, or bleeding causing a decrease in haemoglobin levels by 20 g/L (1.24 mmol/L) or more.

The amount of *wilate* needed and the number of injections necessary to stop the bleed will be documented. The required IU/kg BW per bleeding event will be calculated.

Efficacy of *wilate* will be assessed for all treated BEs, using a 4-point objective haemostatic efficacy scale (i.e. excellent – good – moderate – none) detailed in **Table 3**. In case of minor bleeds treated at home, the assessment should be made by the patients' parents. Major BEs should preferably be treated at the study site. An efficacy assessment will be made by the responsible treating Investigator after the end of the bleeding event, based on the 4-point objective haemostatic efficacy scale.

Table 3 Efficacy Assessment of the Treatment of Breakthrough BEs

Excellent	Bleeding was completely stopped within 3 days in case of minor bleeds, within 7 days in case of major bleeds, and within 10 days in case of gastrointestinal bleeds
Good	Bleeding was completely stopped, but time and/or dose slightly exceeded expectations
Moderate	Bleeding could be stopped only by significantly exceeding time and/or dose expectations
None	Bleeding could be stopped only by using other VWF-containing products

Based on these data, the frequency of BEs, the total, traumatic, and spontaneous ABR under prophylactic treatment will be calculated.

The proportion of BEs successfully treated with *wilate* will be evaluated for all BEs in total and further differentiated by BE severity. All efficacy ratings assessed as either “excellent” or “good” according to the 4-point objective haemostatic efficacy scale will be considered successfully treated.

4. *Efficacy Assessment in Perioperative Prophylaxis*

The following surgery-related parameters will be documented for major surgeries (parameters marked with * are obligatory also for minor surgeries, while the unmarked parameters can be collected for minor surgeries depending on availability).

- Type of surgery (planned or emergency)*
- Location of surgery*
- Severity of surgery (minor, major)*
- Expected and actual duration of surgery
- Expected average/maximum and actual blood loss
- Pre-, intra-, and postoperative *wilate* administration data*
- Pre-, intra-, and postoperative VWF:Ac (VWF:RCo) and FVIII plasma levels
- Routine safety laboratory
- Presence of wound haematomas
- Vital signs (blood pressure, heart rate, body temperature, and respiratory rate)
- Details on concomitantly administered medications (except standard anaesthetics)*
- Blood transfusion requirements
- Brief narrative describing the outcome of the intervention*
- Overall efficacy assessment at the end of the postoperative period by the responsible treating Investigator. Predefined assessment criteria will be used*
- Monitoring of AEs*

Surgeries are defined as major if any of the following criteria are met:

- General or spinal anaesthesia required
- Opening into the great body cavities required
- Severe haemorrhage during surgery possible
- Haemostatic therapy for at least 6 days required
- Orthopaedic interventions involving joints (ankle, knee, hip, wrist, elbow, shoulder)
- Extraction of ≥ 3 teeth
- Surgeries/conditions in which the patient's life is at stake

The classification is made prospectively. All other surgeries are classified as **minor**.

4 STUDY POPULATION

4.1 Population Base

Overall, 12 patients (eight evaluable) with VWD under the age of 6 years suffering from severe VWD defined as screening VWF:RCo <20%, regardless of prior treatment will be enrolled into this study. At least four of these patients should be suffering from hereditary type 3 VWD. The remaining patients can be diagnosed with severe type 2 (except 2N) or severe type 1 VWD.

"Regardless of prior treatment" in this context means that both subjects previously treated with VWF/FVIII-containing products (either on-demand treatment or regular prophylactic treatment) and previously untreated patients (PUPs) can be included in the study.

4.1.1 Inclusion Criteria

Patients who meet all of the following criteria are eligible for the study:

1. Patients aged <6 years at the time of screening
2. Type 3 (at least four patients), severe type 2 (except 2N) or severe type 1 VWD (any of which with VWF:RCo <20%) according to medical history, requiring substitution therapy with a VWF-containing product
3. Minimum body weight 12.5 kg at the time of screening
4. Voluntarily given, fully informed written and signed consent obtained before any study-related procedures are conducted (obtained from the patient's parent(s)/legal guardian(s))

4.1.2 Exclusion Criteria

Patients who meet any of the following criteria are *not* eligible for the study:

1. History, or current suspicion of VWF or FVIII inhibitors
2. Injection of DDAVP or VWF-containing product within 72 hours prior to inclusion
3. Medical history of a thromboembolic event
4. Platelet count <100,000/ μ L at screening (except for VWD type 2B)
5. Patients receiving, or scheduled to receive, immunosuppressant drugs (other than antiretroviral chemotherapy), such as prednisone (equivalent to >10 mg/day), or similar drugs
6. Treatment with any IMP in another interventional clinical study currently or within four weeks before enrolment
7. Other coagulation disorders or bleeding disorders
8. Known hypersensitivity to any of the components of the study drug

4.2 Prior and Concomitant Therapy

4.2.1 Permitted Concomitant Therapy

Vaccination against hepatitis A and B (or the presence of antibodies resulting from a previous infection, or other evidence of immunisation) is strongly recommended before repeated treatment with a VWF/FVIII concentrate such as *wilate*.

Patients receiving, or scheduled to receive, immunosuppressant drugs (other than antiretroviral chemotherapy), such as prednisone (equivalent to >10 mg/day), or similar drugs may not be enrolled.

Concomitant therapies not interfering with the objectives of the study are permitted. Details of any concomitant medication must be recorded in the electronic Case Report Form (eCRF).

4.2.2 Forbidden Concomitant Therapy

No VWF/FVIII concentrates other than *wilate* must be administered (except for emergency situations). Patients permanently switching to other VWF/FVIII products within the study participation period will be assessed as treatment failures in the efficacy analyses.

However, there are exceptions to this rule. Patients will hence not be considered treatment failures in the efficacy analyses, if:

- the use of another VWF/FVIII concentrate was due to an emergency case (example: in the case of an accident causing a bleeding that requires treatment with VWF concentrate but without access to the IMP, a different concentrate may be used instead)
- the IMP was not available for the patient in time (example: patient experiences a severe bleed but parents do not have enough product available).

4.3 Withdrawal and Replacement of Subjects/Patients

4.3.1 Premature Subject/Patient Withdrawal

Parents have the right to withdraw their children from the study at any time for any reason, without the need to justify their decision. The Investigator also has the right to withdraw subjects/patients in case of AEs, poor compliance, or other reasons. Since an excessive rate of withdrawals can render the study noninterpretable, any unnecessary withdrawal of subjects/patients should be avoided.

For any withdrawals after study entry, the Investigator will obtain all the required details and document the reason(s) for discontinuation. If the reason for withdrawal of a patient is an AE, the main specific event or laboratory test will be recorded, and the Investigator will make thorough efforts to clearly document the outcome.

4.3.2 Subject/Patient Replacement Policy

Patients withdrawn from the study for safety reasons will not be replaced.

4.4 Assignment of Subjects/Patients to Treatment Groups

The Investigator will enter a unique identifier (consisting of the study code (SC), centre code (CC), and patient number (PN), in the format “SC-CC-PN”) of each patient in both the CRF and the confidential patient identification list. The Investigator will inform the monitor of new patients enrolled.

Under no circumstances are patients who enrol in the study permitted to re-enrol.

4.5 Relevant Protocol Deviations

Deviations from the protocol should be avoided at all times throughout the study. If deviations occur, the Investigator should promptly inform the monitor, and the implication of the deviation must be assessed and discussed. Any deviation must be documented, stating the reason and date and the action taken. The documentation must be kept in the Investigator’s study file and the Sponsor’s study master file. A complete list of all critical, major and minor deviations will be compiled and regularly updated by the Project Manager and provided for preparation of the Clinical Study Report (CSR).

All cases where the time windows for visits to the study centres are exceeded due to COVID-19-related illness on the part of patients/parents or study staff will be defined as a minor deviation.

In case of any major protocol deviation, the Investigator and Octapharma will decide on the further participation of the subject/patient in this study after having discussed all relevant aspects.

Examples of critical/major protocol deviations are:

- Patients who entered the study even though they did not satisfy the eligibility criteria.
- Patients who received the wrong treatment or incorrect dose (also see **Section 5.4**).
- Patients with substantial deviations from the prophylactic treatment regimen.
- Patients who received forbidden concomitant medication.

4.6 Subsequent Therapy

All patients who leave the study – be it prematurely or per protocol (PP) – will continue VWD treatment as per the discretion of the responsible treating Investigator.

5 INVESTIGATIONAL MEDICINAL PRODUCT(S)

5.1 Characterisation of Investigational Product(s)

The VWF/FVIII concentrate *wilate*, produced from the plasma of human donors, is presented as a powder and solvent for intravenous injection containing nominally 500 IU or 1000 IU human VWF and human FVIII per vial. The ratio between VWF ristocetin co-factor activity (VWF:RCo) and FVIII:C is 1:1.

The product contains approximately 100 IU/mL human VWF when reconstituted with 5 mL/10 mL water for injections with 0.1% polysorbate 80. The specific activity of *wilate* is ≥ 67 IU VWF:RCo/mg protein.

The injection or infusion rate should not exceed 2–3 mL per minute.

5.2 Packaging and Labelling

Final labelling of the IMP will comply with the national requirements of each country where the study is conducted.

5.3 Conditions for Storage and Use

The powder and solvent vials must be stored in a refrigerator at +2°C to +8°C (36°F to 46°F). The vials must be kept in the outer carton to protect from light and must not be frozen.

As an accepted exception to the storage conditions, the product can be stored at room temperature (max. +25°C or 77°F) for a maximum of 2 months.

After reaching room temperature, however, no return to refrigerated conditions is permitted.

2 months after the product is taken out of the refrigerator for the first time it must not be used any more and must be destroyed following local rules.

The Investigator and any authorised personnel at the site will ensure that the IMP is stored in appropriate conditions with restricted access and in compliance with national regulations.

5.4 Dose and Dosing Schedule

5.4.1 *wilate* Dosage for PK Assessment

For the PK Assessment, a single dose of 80 IU/kg BW will be administered, based on the weight measured at the beginning of the visit. The exact dose calculated according to the nominal potency should be administered, with 70–85 IU/kg BW as the acceptable range. The injection or infusion rate should not exceed 2–3 mL per minute. At least three different *wilate* batches will be used.

As regards determining incremental in-vivo recovery over time, a single dose of *wilate* is administered at the dose of regular prophylactic treatment.

5.4.2 *wilate* Dosage for Prophylactic Treatment

For prophylactic treatment, *wilate* should be administered 2–3 times per week at a recommended dose of 30–50 IU/kg BW over 12 months. The prophylactic dose and frequency

for each patient will be determined by the responsible treating Investigator, based on the individual patient's clinical condition.

After each body weight measurement during the study, dose adjustments based on the patient's actual weight should be considered.

The first prophylactic dose will be administered after completion of the PK Assessment, i.e. after the 72-hour sample has been collected), and should be administered at the study site before patients return to home treatment. The same venipuncture as that used to collect the sample can be used for administration (taking into account prior rinsing with NaCl).

It is recommended to aim for a dose that supports the administration of full vials of *wilate* during home treatment. However, the administration of partial vials is permitted if clinically indicated, as long as the recommended dose range is respected. Such cases must be carefully discussed and explained in detail with the patients' parents and must be accurately documented in the patient's diary and in the eCRF. Parents should be trained in the administration of partial vials and their return after use.

In case of unacceptably frequent breakthrough BEs (i.e. two or more BEs within a 30-day period or one major BE), the dose of *wilate* should be increased by approximately 5 IU/kg BW (depending on the vial size of the additional vial(s) that need(s) to be injected) and/or the treatment frequency can be increased. This rule applies irrespective of whether one or more bleeding sites are affected, and for BEs that occur on the same day.

5.4.3 *wilate* Dose for the Treatment of Bleeding Episodes (BEs)

The dose (and duration) of treatment of BEs will depend on the location and extent of bleeding and on the clinical condition of the patient.

Generally, 1 IU/kg BW VWF:Ac and FVIII:C raises the plasma level by 1.5–2% of normal activity for the respective protein, but this increase may be lower in children below the age of 6 years. Usually, about 20–50 IU/kg BW *wilate* are necessary to achieve adequate haemostasis. This will raise the VWF:Ac and FVIII:C in the patients by approximately 30–100% [12].

Recommendations for the dosing in the treatment of BEs in paediatric patients under 6 years of age has been adapted from the US Package Insert [13] and is shown in **Table 4**.

Table 4 *wilate* Dosage Recommendations for the Treatment of BEs

Dose Type	Minor haemorrhage	Major haemorrhage
Loading dose	30–50 IU/kg BW	50–80 IU/kg BW
Maintenance dose	30–40 IU/kg BW every 12–24 hours	30–50 IU/kg BW every 12–24 hours
Therapeutic goal	Maintain VWF:Ac and FVIII:C trough levels >30%	Maintain VWF:Ac and FVIII:C trough levels >50%

After the initial treatment phase of a BE, any further treatment to avoid re-bleeding is to be documented as “prophylactic treatment to avoid re-bleeding” until the transition to the regular prophylactic treatment schedule.

5.4.4 *wilate* Dose for Surgical Prophylaxis

For prevention of bleeding in case of surgery, VWF:Ac peak levels of 50% should be achieved for minor surgeries and VWF:Ac peak level of 100% should be achieved for major surgeries.

An appropriate dose should be re-administered every 12–24 hours of treatment. The dose and duration of the treatment depend on the clinical status of the patient, the type and severity of bleeding, VWF:Ac and FVIII:C levels.

In patients receiving FVIII-containing VWF products, plasma levels of FVIII:C should be monitored to reveal sustained excessive FVIII:C plasma levels, which may increase the risk of thrombotic events. Accordingly, FVIII activity levels should not exceed 200%.

Recommendations for the dosing in surgical prophylaxis in paediatric patients under 6 years of age has been adapted from the US Package Insert [13] and is shown in **Table 5**.

Table 5 *wilate* Dosage Recommendations for Surgical Prophylaxis

Dose type	Minor surgeries (including tooth extractions)	Major surgeries
Loading dose	40–60 IU/kg BW	60–80 IU/kg BW
Maintenance dose	20–30 IU/kg BW, or half the loading dose, every 12–24 hours for up to 3 days	30–40 IU/kg BW, or half the loading dose, every 12–24 hours for up to 6 days or longer
Therapeutic goal	Achieve VWF:Ac peak levels of 50% after loading dose and trough levels of >30% during maintenance doses	Achieve VWF:Ac peak level of 100% after loading dose and trough levels of >50% during maintenance doses

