- Severity of surgery (minor, major) (see definitions under (a) below)*
- Expected and actual duration of surgery
- Expected average/maximum and actual blood loss

- Pre-, intra-, and postoperative *wilate* administration data (see definitions under **(b)** below)*
- Pre-, intra-, and postoperative VWF:Ac (VWF:RCo) and FVIII plasma levels (see definitions under **(b)** below)
- Routine safety laboratory
- Presence of wound haematomas
- Vital signs (blood pressure, heart rate, body temperature, and respiratory rate)
- Details on concomitantly administered medications (except standard anaesthetics)*
- Blood transfusion requirements
- Brief narrative describing the outcome of the intervention*
- Overall efficacy assessment at the end of the postoperative period by the responsible treating Investigator. Predefined assessment criteria will be used (see below)*
- Monitoring of AEs*

Details regarding the time points of data collection and assessments for surgical prophylaxis are described below in **Table 6**.

The efficacy of *wilate* will be assessed at end of the postoperative period by the responsible treating Investigator, using predefined assessment criteria.

(a) Severity of surgery

Surgeries are defined as major if any of the following criteria are met:

- General or spinal anaesthesia required
- Opening into the great body cavities required
- Severe haemorrhage during surgery possible
- Haemostatic therapy for at least 6 days required
- Orthopaedic interventions involving joints (ankle, knee, hip, wrist, elbow, shoulder)
- Extraction of ≥ 3 teeth
- Surgeries/conditions in which the patient's life is at stake

The classification is made prospectively. All other surgeries are classified as minor.

(b) Definitions of periods and time points before, during, and after surgery

- Preoperative is defined as the time period of up to 3 hours before the start of surgery.
- The end of surgery is defined as the time immediately after the last surgical suture.
- Postoperative is the period from the end of surgery to the time the patient returns to his or her regular VWF treatment regimen.
- The end of the postoperative period is the time the patient returns to his or her regular VWF treatment regimen.

Table 6 Assessments for Perioperative Prophylaxis

Assessment	For details, see Section	Within 12 hours before start	Within 3 hours before start	Surgery		POP day 1	Any POP day	End of POP period
				Intra-operatively	End [1]			
Body weight		x						

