For minor surgeries, the overall assessment of perioperative prophylaxis will be assessed by the responsible Investigator using the excellent, good, moderate, and none scale, taking the postoperative assessment in to account as shown in **Table 8**.

Joint Health Status

Joint health will be assessed using the Haemophilia Joint Health Score (HJHS) [16], which has been specifically validated for the assessment of clinical outcome in adult patients with VWD (mean age 46 years [range 18–80]) [11].

The HJHS has shown excellent reliability and good validity in both adults and children with haemophilia [16-18].

Target joint(s) will also be documented. Target joint(s) are defined as having three or more spontaneous BEs into a single joint within six consecutive months preceding either the Screening Visit or the Study Completion Visit.

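### For an extraction of three or more teeth, or any extraction under general or spinal anaesthesia, the protocol points to two different surgical dosing columns

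*Protocol*

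**What the plan says.** **Dosing.** Protocol section 5.4.4 gives surgical dosing in Table 5, with one column for minor and one for major surgery. The first column is headed "Minor surgeries (including tooth extractions". The synopsis repeats the table with the same heading. Neither copy limits the number of teeth or refers to the severity definition. Maintenance in the minor column is "20–30 IU/kg BW, or half the loading dose, every 12–24 hours for up to 3 days"; in the major column it is "30–40 IU/kg BW, or half the loading dose, every 12–24 hours for up to 6 days or longer".

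**Severity.** Sections 3.3.3 and 7.2.2(a) carry the same list of criteria. In 7.2.2(a): "Surgeries are defined as major if any of the following criteria are met". The list includes "Extraction of ≥ 3 teeth" and "General or spinal anaesthesia required". It closes: "The classification is made prospectively. All other surgeries are classified as minor".

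**Assessment and scoring.** Section 7.2.2 asks for an efficacy rating at the end of surgery after major surgeries. Under Table 6, VWF:Ac and FVIII:C sampling around the first three postoperative doses is mandatory only for major surgery. The overall rating for major surgery combines the intraoperative and postoperative ratings through Table 9. For the other class, "For minor surgeries, the overall assessment of perioperative prophylaxis will be assessed by the responsible Investigator" from the postoperative criteria in Table 8 alone.

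**SAP.** Section 4.7.2 takes the definition of surgical severity from the protocol. It restricts the surgery analysis to the case of more than 3 treatment-emergent surgeries; otherwise the data are only listed.

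**The concern.** Tooth extraction is the only procedure that Table 5 names, and it is named without qualification. A clinician dosing from section 5.4.4 finds extractions under minor surgery. The same clinician completing the surgery record under 7.2.2(a) must class an extraction of three or more teeth as major, and likewise an extraction of one or two teeth if general or spinal anaesthesia is needed.

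The first thing at stake is that one operation in a child under 6 carries two stated dosing recommendations and two sets of plasma-level goals. The second is coherence of the data: a procedure dosed from one column may be sampled and scored under the rules for the other class, and the surgery data would not show openly that this had happened.

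**Working it through.** The plan gives no figure to reproduce here. The check sets the passages side by side and then asks what depends on the class.

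**1. Class of an extraction under each passage**

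| Procedure | Table 5 / synopsis heading | 3.3.3 and 7.2.2(a) |
|---|---|---|
| 1–2 teeth, no major criterion met | Minor | Minor |
| 1–2 teeth, general or spinal anaesthesia | Minor | Major |
| 3 or more teeth | Minor | Major |

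The passages disagree in the last two rows.

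**2. Distance between the columns** (Table 5)

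For two ranges, the overlap runs from the larger of the lower limits to the smaller of the upper limits.

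| Item | Minor | Major | Overlap |
|---|---|---|---|
| Loading, IU/kg | 40–60 | 60–80 | max(40, 60) = 60 to min(60, 80) = 60: one point |
| Maintenance, IU/kg | 20–30 | 30–40 | max(20, 30) = 30 to min(30, 40) = 30: one point |
| Duration | up to 3 days | up to 6 days or longer | – |
| VWF:Ac peak goal | 50% | 100% | none stated in common |
| VWF:Ac trough goal | >30% | >50% | – |

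The stated dose ranges touch only at their boundaries, so in general a dose chosen from one column lies outside the other.

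**3. What follows the 7.2.2 class**

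The end-of-surgery rating, the mandatory postoperative sampling and the choice between Table 9 and Table 8 all sit in section 7.2.2 with the severity definition. None refers to the Table 5 heading. Read literally, an extraction of three or more teeth takes the minor dosing column and the major assessments and scoring.

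**4. What would happen if a site took the class from the dosing heading**

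This is conditional on a misreading. Table 9 (major rule) is compared with the postoperative rating alone (minor rule). Success is excellent or good, as in SAP section 6.1. E, G, M and N are excellent, good, moderate and none; each cell shows the Table 9 result, and bold marks a change in success status.

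| Intraoperative | Post E | Post G | Post M | Post N |
|---|---|---|---|---|
| E | E | G | **G** | M |
| G | G | G | M | M |
| M | G | **M** | M | N |
| N | **M** | **M** | N | N |

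- The overall rating differs from the postoperative rating in 2 + 2 + 2 + 3 = 9 of 16 cells, counting row by row.
- Success status changes in 4 of 16. E/M is a success under Table 9 but not under the postoperative rating alone. M/G, N/E and N/G are non-successes under Table 9 but successes under the postoperative rating alone.

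The 16 cells are not equally likely, so 4 of 16 is a count of combinations and not a probability of error.

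**The case against.** The best defence is a harmonising reading: the parenthesis in Table 5 only gives an example of minor surgery, and the specific rule in 3.3.3 and 7.2.2(a) decides the class. The text of 5.4.4 sets peak goals for minor and major surgery without redefining either. Table 5 contains recommendations, and the section lets dose and duration depend on the patient's clinical status. This reading is reasonable, but Table 5 does not state it or point to the definition. The need for a clarification stands.

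The defence succeeds against three stronger readings.

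- A reader might infer that the same operation is assigned two efficacy algorithms. It is not. Severity has one definition, applied prospectively; Tables 8 and 9 sit beside it, and the SAP defers to it. An extraction of three or more teeth goes to Table 9. The 4-of-16 count applies only if a site wrongly takes the class from the dosing heading.
- A reader might infer that an analysis of surgical efficacy by severity is compromised. None is planned. Protocol section 9.2.2.4 provides one distribution of ratings over all procedures, with severity described; the planned efficacy breakdown by severity is for bleeding episodes.
- A reader might infer a direct effect on the primary endpoint. The tABR excludes bleeds in surgery periods whatever the class. The surgery period in SAP section 6.1 runs to the last surgical dose actually given, so any influence of the dosing column is indirect.

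**Conclusion.** The contradiction is real and appears in both copies of the dosing table and both copies of the definition. For an extraction that meets a major criterion, the documents point to two dosing columns that differ in every row and share only the boundary doses of 60 IU/kg (loading) and 30 IU/kg (maintenance). The direct consequence is that a procedure can be dosed as minor while it is classified, sampled and scored as major.

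The statistical effect is limited. Scoring follows a single class, surgical efficacy is a descriptive secondary endpoint in up to 12 children, and it is summarised only if more than 3 surgeries occur. The documents do not say how many extractions took place or which column any site used, so the effect on the reported results cannot be sized. The point is still more than clerical, because conflicting dosing goals are stated for the same operation in young children.

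**What to change.** Reconcile the Table 5 heading and its synopsis copy with the severity definition in 3.3.3 and 7.2.2(a), so that one prospectively assigned class governs the dosing column, the mandatory assessments and the scoring. Which class and which dosing apply to dental extractions is for the sponsor's clinicians to decide.

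The SAP needs no new rule on class, because section 4.7.2 already takes severity from the protocol. As an option, list for each dental procedure the dosing column followed, using the administration data and the outcome narrative that are obligatory for minor and major surgeries alike. The number of teeth is not among the listed surgery data items, so this listing should not depend on it.

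The cost is a wording change in two table headings, through the usual amendment route, and at most one extra listing. No new data collection is required.
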